9.6.2 Exposure to Investigational Product

Details for each AMG 966 administration will be listed for every subject. In addition a listing of the unique manufacturing lot numbers, and a listing of the subjects administered each manufacturing lot number will be provided.

Descriptive statistics will be produced to describe the exposure to investigational product by dosing schedule. Number of cycles, number of doses of investigational product and the total dose by unit will be summarized. Summaries of the number and percentage of subjects with dose modifications and reason for modification will be provided.

9.6.3 Exposure to Concomitant Medication

All medication will be coded using the WHO drug dictionary. A subject listing of all prior and concomitant medications will be presented.

9.7 Exploratory Endpoints

The statistical analysis in this section will be considered exploratory and will be performed only when deemed appropriate. Details of analysis will be provided in supplemental analysis plan for exploratory biomarker analysis. Relationships between the PK and the markers for safety and efficacy may also be explored.

9.8 Other Analyses

All other analyses will be covered in a separate analysis plan.

9.8.1 Analyses of Pharmacokinetic or Pharmacokinetic/Pharmacodynamic Endpoints

9.8.1.1 Pharmacokinetic Endpoints

PK parameters will include, but are not limited to maximum observed concentration (C_{max}), minimum observed concentration (C_{min}) and area under the concentration-time curve over the dosing interval [AUC] and if feasible half-life ($t_{1/2}$).

The PK parameters of AMG 224 conjugated antibody, Total anti-BCMA antibody, and DM1 will be estimated using standard noncompartmental methods and summarized by dose level using means, standard deviations, medians, minimums and maximums.

Serum concentrations below the lower limit of quantifications will be set to zero for the estimation of the pharmacokinetic parameters for each subject and for the calculation of the summary statistic for each time point. Actual dosing and sampling time will be used for all calculations. The reasons for excluding any sample from the analyses will be provided.

Individual concentration-time data will be summarized by dose level. AMG 224 conjugated antibody, Total anti-BCMA antibody, and DM1 concentrations at each time point along with PK parameter values may be listed for each subject. Individual concentration-time data will be tabulated and presented graphically. Summary statistics will be computed for each sampling time and parameter as appropriate.

Analysis of the relationship between AMG 224 dose and exposure parameters (AUC and C_{max}) will be conducted and plots of the relationship between AMG 224 dose and exposure parameters along with dose proportionality assessment will be provided.

Analysis of the relationship between AMG 224 conjugated antibody concentrations and change from baseline in QTcF will be conducted and plots of the relationship between AMG 224 conjugated antibody concentrations and change from baseline in QTcF will be

provided. The above analysis will also be conducted for the Total anti-BCMA antibody, and DM1.

Additional analyses to explore relationship between exposure and safety and exposure and efficacy may also be performed.

10. Changes From Protocol-specified Analyses

There are no changes to the protocol-specified analyses.

11. Literature Citations / References

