Preliminary PK results of AMG 224 following administration as an IV infusion Q3W to adult subjects with relapsed or refractory multiple myeloma in ongoing FIH study are available for 12 subjects after the first dose of 30 mg (3 subjects), [REDACTED] (3 subjects), [REDACTED] (3 subjects), and [REDACTED] (3 subjects). Mean serum concentration-time profiles

for AMG 224 conjugated antibody, total anti-BCMA antibody, and DM1 are shown in Figure 1.

Figure 1. Preliminary Serum Concentration-time Profiles of AMG 224 Conjugated Antibody, Total Anti-BCMA Antibody, and DM1 in Subjects With Relapsed or Refractory Multiple Myeloma Following Q3W Administration of AMG 224 as IV Infusion

Ab = antibody; BCMA = B cell maturation antigen; IV = intravenously; LLOQ = lower limit of quantitation; Q3W = once every 3 weeks

Mean (+ SD) concentration-time profiles: n = 3 subjects each dose cohort (30 mg Q3W, [redacted] Q3W; [redacted] Q3W; [redacted] Q3W)

Analytes:

- AMG 224 conjugated Ab = anti-BCMA Ab with at least 1 DM1 molecule conjugated to the Ab
- Total anti-BCMA Ab = sum of unconjugated anti-BCMA Ab plus AMG 224 conjugated Ab
- DM1 = unconjugated total DM1

DM1 LLOQ 0.25 ng/mL: DM1 levels following administration of 30 mg and [redacted] doses were below LLOQ.

IC_{90} KMS26: AMG 224 conjugated Ab concentration expected to result in 90% killing of tumor cells estimated from the pharmacokinetic/pharmacodynamic modeling of AMG 224-mediated tumor burden reduction observed in orthotopic xenograft (BCMA-expressing human multiple myeloma [KMS26]) mice.

Source: Pharsight Knowledgebase Server: <http://uslv-pweb-pks02/pks/WebUI> Study: 20130314_BSMLIMSPLUS_Clinical_v1

Following Q3W IV administration of AMG 224 to subjects with relapsed or refractory multiple myeloma, similar pharmacokinetic profiles were observed over the 3-week dosing interval for AMG 224 (anti-BCMA antibody with at least 1 DM1 molecule conjugated to the antibody) and total anti-BCMA antibody (sum of AMG 224 plus unconjugated anti-BCMA antibody), indicating low levels of circulating unconjugated antibody. In addition, low plasma levels were observed for DM1 (total unconjugated DM1). The DM1 levels following administration of AMG 224 30 mg or [redacted] doses were below the lower limit of quantitation (LLOQ) (0.25 ng/mL); and following administration of

██████████ dose were close to the LLOQ, with mean maximum observed concentrations of 0.31 ng/mL and 0.52 ng/mL, respectively.

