Approved

Footnotes defined on the next page.

1. Clinical evaluation will include: physical exam with a neurologic assessment, ECOG status, and weight. Screening only - medical and surgical history, weight and height.
2. Vitals signs (blood pressure, respiratory rate, heart rate, temperature) will be collected (pre-dose on dosing days) after subject has rested for at least 5 minutes.
3. ECG will be performed after subject has rested for approximately 5 minutes; X1 = single ECG; X3 = triplicate ECG (tracings one minute apart), reporting PR, QRS, QT, QTc, RR interval. If interval prolongation > 480 msec occurs (and is a 30 msec increase above baseline), subject's serum potassium, magnesium, calcium and phosphorus should be measured immediately and replaced if needed. On day 1 predose only, triplicate ECGs to be completed at approximately 90, 60 and 30 minutes prior to dosing.
4. Echocardiogram (or MUGA; a consistent method will be used throughout the study) will be performed at screening only.
5. Refer to [Appendix H](#) for the evaluation tool and document in the eCRF. The site will enter the score to each question and the total score will be derived in RAVE.
6. Each complete cycle will be of 3 weeks duration comprising 1 dose administration of AMG 224. The subsequent cycle will start 3 weeks after the dose administration of the prior cycle
7. AMG 224 PK = samples collected and analyzed for AMG 224 conjugated antibody and Total anti-BCMA antibody. The PK of AMG 224 conjugated antibody and total anti-BCMA antibody will be assessed using the same samples.
8. DM1 PK = samples collected and analyzed for Total unconjugated DM1 PK. Samples for total DM1 PK will be collected on Day 1: predose, 0.5hr, EOI, 4hr, 24hr (Day 2), 96hr (Day 5); Day 22: predose, 0.5hr, EOI, 4hr, 24hr (Day 23), 96hr (Day 26). Refer to Laboratory Manual for procedure.
9. PK samples should be collected at the exact nominal time point as noted. If unable to collect a PK sample at the specified nominal time point collect it as close as possible to the nominal time point and record the actual collection time. PK samples not collected at exact nominal time point will not be considered protocol deviations.

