4.2 Subgroups

Biomarker data may be incorporated in additional exploratory subgroup or multivariate analyses. The analyses of biomarkers may be performed after collection of all samples

during the conduct of the study and therefore may be reported after the primary analysis of efficacy endpoints.

5. Definitions

Age at Enrollment

Subject age at enrollment will be determined using the age in years reported in the clinical database.

AUC_{0-3 week} = AUC_{0-504 hrs}

It is defined as the area under the concentration-time curve from time 0 to 504 hours.

Baseline

Unless otherwise specified the baseline value for parameters/assessments scheduled to be performed on the same day as the first administration of AMG 224 (Q3W), is the last value measured before the first administration of AMG 224 on that day. For parameters/assessments not scheduled to be performed (or scheduled but not performed) on the same day as the first administration of AMG 224, the baseline value is the value from the screening period measured closest to the day of first administration of AMG 224. In the event that multiple assessments are done on the same day as the first administration of AMG 224 and there is no time associated with the assessments, the value associated with the last clinically planned event before the first administration of AMG 224 will be used as the baseline value.

For baseline ECG, three triplicate ECGs to be collected ≥ 30 minutes apart, with each ECG in triplicate approximately 30 seconds apart (3 set collected predose on day 1 with total of 9 ECGs) planned to be taken predose. Mean value will be calculated and used in the analysis. The mean of the values within a triplicate should be calculated before taking the mean of the triplicate averages. Where an ECG is missing within a triplicate, all available data will be averaged for that time point.

Best Overall Response

Best overall response for a subject is the best observed post baseline disease response per the International Myeloma Working Group Uniform Response Criteria for Multiple Myeloma (IMWG-URC).

Best Overall Response/Progression CRF will be employed to determine the response.

Every effort should be made to document the objective progression even after discontinuation of treatment.

Body Mass Index (BMI)

Body Mass Index should be calculated using the following formula

$$\text{BMI (kg/m}^2\text{)} = \text{weight (kg)} / [\text{height (cm)} / 100]^2$$

Change From Baseline

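### For DM1, whose reported levels lie below or close to the assay limit, setting BLQ values to zero in a 0–504 h AUC biases the dose-proportionality assessment, and the DM1–QTcF analysis has no stated BLQ rule

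*SAP*

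**What the plan says.** SAP 9.8.1.1 applies one non-compartmental analysis to AMG 224 conjugated antibody, total anti-BCMA antibody and DM1. Its BLQ rule reads: "Serum concentrations below the lower limit of quantifications will be set to zero for the estimation of the pharmacokinetic parameters for each subject". The same sentence extends the rule to the summary statistics per time point.

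The AUC in that section is over the dosing interval. SAP Section 5 sets AUC0–3 week equal to AUC0–504 hrs: "It is defined as the area under the concentration-time curve from time 0 to 504 hours". A dose-proportionality assessment on AUC and Cmax is a commitment, not an option. After describing the conjugate's concentration–QTcF analysis, the section adds: "The above analysis will also be conducted for the Total anti-BCMA antibody, and DM1".

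Protocol 2.4.2 reports preliminary first-dose PK for 12 subjects, 3 in each of four cohorts, and gives a DM1 LLOQ of 0.25 ng/mL. DM1 was below that limit after 30 mg and after one redacted dose. In the other two cohorts, levels "dose were close to the LLOQ, with mean maximum observed concentrations of 0.31 ng/mL and 0.52 ng/mL, respectively" (the dose itself is redacted).

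The DM1 sampling times are in footnote 8 to Protocol Table 5: "Samples for total DM1 PK will be collected on Day 1: predose, 0.5hr, EOI, 4hr, 24hr (Day 2), 96hr (Day 5"). The footnote gives the same six nominal times from Day 22, ending at 96 h (Day 26), and lists nothing later.

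**The concern.** The rule may do no harm for an analyte that stays well above its assay limit for most of the interval. The protocol's own data show that DM1 did not do so in the four reported cohorts. With zeros in place of censored values, the computed AUC depends on how many samples happen to cross 0.25 ng/mL as well as on exposure. That number rises with dose, so AUC appears to rise faster than it does.

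DM1 is the cytotoxic payload and its PK is a secondary endpoint. A false signal of more-than-proportional payload exposure, or a table showing zero exposure where the truth is only below the assay limit, could mislead later dose work. For DM1–QTcF the problem is different: the SAP commits to the analysis without saying how BLQ values enter it.

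**Working it through.** **Inputs.** From the documents: LLOQ 0.25 ng/mL and mean DM1 peaks 0.31 and 0.52 ng/mL (Protocol 2.4.2); sampling at predose, 0.5 h, end of infusion (taken as 1 h), 4, 24 and 96 h, with Day 22 predose serving as the 504 h point of cycle 1 (Table 5, footnote 8); BLQ = 0 (SAP 9.8.1.1). The documents give no DM1 half-life, so it is assumed and varied.

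**Window.** 3 × 7 × 24 = 504 h, which reproduces the SAP definition. The unsampled stretch is 504 − 96 = 408 h, or 408/504 = 81% of the interval.

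**Distance from the limit.** 0.31/0.25 = 1.24 and 0.52/0.25 = 2.08. With mono-exponential decline, levels stay above the LLOQ for log2(1.24) = 0.31 and log2(2.08) = 1.06 half-lives after the peak.

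**Share of AUC below the LLOQ.** Post-peak AUC is Cmax/k, and the part after the LLOQ is crossed is LLOQ/k. The share is LLOQ/Cmax at any half-life: 0.25/0.31 = 81% and 0.25/0.52 = 48%.

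**All-BLQ profiles.** Cmax and AUC are zero by rule. CL, which Protocol 10.4.3 lists for DM1, is then undefined.

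**Weight of one sample.** The 96–504 h trapezoid with a zero at 504 h is 0.5 × 408 × C96 = 204 × C96. At C96 = 0.25 it is 51 ng·h/mL; just below the LLOQ it is zero. At the mean peaks, AUC0–96 cannot exceed 0.31 × 96 = 29.8 or 0.52 × 96 = 49.9 ng·h/mL.

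**Effect on the ratio of the two cohorts.** If half-life does not depend on dose, the true ratio is 0.52/0.31 = 1.68. I simulated log-normal peaks with 40% CV around the two reported means, a 1 h infusion, mono-exponential decline, the sampling times above, BLQ = 0 and the linear trapezoid. The last column stops at the last quantifiable sample. Ratios of mean AUC:

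| Assumed half-life (h) | AUC0–504, SAP rule | AUC0–96, BLQ = 0 | AUC to last quantifiable |
|---|---|---|---|
| 6 | 3.1 | 3.1 | 3.3 |
| 12 | 2.7 | 2.7 | 3.4 |
| 24 | 3.6 | 3.6 | 4.5 |
| 48 | 3.1 | 2.9 | 3.4 |
| 72 | 4.0 | 2.8 | 4.2 |
| 96 | 4.0 | 2.8 | 4.0 |
| 192 | 3.0 | 2.5 | 3.0 |

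On the same times without censoring, the ratio is 1.68 at every half-life, so zeroing causes the distortion of this ratio. AUC0–96 helps modestly, and only at half-lives where C96 can be quantifiable. AUC to the last quantifiable time is no better and often worse.

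**LLOQ/2 instead of zero.** An all-BLQ profile gives 0.125 × 504 = 63 ng·h/mL whatever the dose, so this substitution is no remedy.

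**The case against.** Several points on the other side have force.

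- **Existing safeguards.** SAP 6.2.1 drops subjects with too few data points, half-life is reported only where feasible, and Appendix F sends PK and PK/PD modelling methods to a separate plan. None of these overrides the rule. No minimum number is given, a zeroed sample can count as a data point, and the zero rule for the non-compartmental analysis is fixed in this SAP.
- **Reach of the data.** A reader might infer that DM1 is at or below the LLOQ in all four cohorts and beyond, so that every DM1 AUC is set by the assay. The documents do not support this. Two mean peaks exceed the LLOQ, by 24% and 108%. Protocol Table 2 lists eight cohorts and DM1 levels are given for four. If exposure rises with dose, censoring shrinks.
- **QTcF.** A reader might infer that undetected DM1 enters the QTcF analysis as zero. The rule names PK parameters and time-point summaries only, and no regression is specified; SAP 9.6.1.5 describes a graphical exploration. The defect is an omission.
- **Larger fold figures.** Much steeper apparent rises can be produced by adding a later cohort, but only with a peak that no document reports. At an assumed mean peak of 1.5 ng/mL and a 48 h half-life, AUC0–504 is about 151 with zeroing and 161 with no censoring, against a true 105. That inflation comes from sparse trapezoids, not from the BLQ rule.
- **The 51 ng·h/mL step.** It is not always inflation. For a subject at the mean peak, C96 reaches 0.25 only at half-lives of about 306 h (peak 0.31) or 90 h (peak 0.52). The true 96–504 h area is then about 66 or 31 ng·h/mL, so 51 is too low in one case and too high in the other. What stands is that one sample decides it.
- **Sampling.** Table 6 lists about 16 DM1 collections, whereas footnote 8 yields 6 + 6 = 12, so later samples may exist.

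**Conclusion.** The point holds for the four reported cohorts. As written, all-BLQ cohorts receive a DM1 exposure of zero. Between the two quantifiable cohorts, a true 1.7-fold difference appears as about 3- to 4-fold (2.7 to 4.0 over half-lives of 6–192 h), biasing the dose-proportionality assessment towards more than proportional. In addition, 81% of the AUC window rests on two samples in cycle 1, and cycle 2 has no listed end-of-interval DM1 sample.

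The size rests on an assumed half-life, 40% CV and mono-exponential decline, and on reading the reported peaks (n = 3 each) as true means. The 81% and 48% shares need only the decline shape and those peaks. For later cohorts and the expansion the size is unknown. DM1 PK is a secondary descriptive endpoint and nothing in the plan bases the MTD on it, so this should be changed but does not threaten the primary objective.

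**What to change.** In SAP 9.8.1.1, for DM1 only:

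1. Report the number and percent BLQ by dose and time point, with Cmax and AUC0–96h in place of AUC0–504. Do not base dose proportionality on AUC to the last quantifiable time, which carries the same censoring bias.
2. Show AUC, Cmin, CL and half-life as not estimable, not as zero, for subjects below a prespecified minimum number of quantifiable post-dose samples (for example 3) and for all-BLQ cohorts. Give the number contributing to each summary, because the subjects who remain are the more highly exposed. In the simulation above, 8–56% of subjects at a mean peak of 0.31 would qualify.
3. Treat BLQ as left-censored at 0.25 ng/mL in the DM1 dose–exposure and DM1–QTcF models, and say so for QTcF, where no rule now exists.

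Keep BLQ = 0 for the two antibody analytes. Reconcile Table 6 with footnote 8 on the number of DM1 samples, and the SAP rule's reference to serum with the mention of plasma DM1 levels in Protocol 2.4.2.

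The cost is SAP wording and a little programming, with no new samples. The price is that no full-interval DM1 AUC is reported. Because AUC0–96h removes only part of the bias, the left-censored model should carry the dose-proportionality conclusion.

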1 = Impute the date of first dose

2 = Impute the first of the month

3 = Impute January 1 of the year

4 = Impute January 1 of the stop year

Note: For subjects who were never treated (first dose date is missing), partial start dates will be set to the first day of the partial month.

Note: If the start date imputation leads to a start date that is after the stop date, then do not impute the start date.

Code Fragments:

Provisional Code Fragments for calculating a confidence interval using the Clopper Pearson Method. The following example SAS code will be utilized for the response rate

analysis providing the proportion of subjects responding to treatment with corresponding 80% confidence intervals.

```
data propci (keep = ns p low_ci upp_ci);  
n=xx; * total n within the treatment group;  
do ns= xx; *number of responders;  
p=ns/n; * response rate;  
q=1-p;  
lowF=FINV(0.1, 2*ns, 2*(n-ns+1)); /* use for 2-sided 80% CI */  
UppF=FINV(1-0.1, 2*(ns+1), 2*(n-ns)); /* use for 2-sided 80% CI */  
low_ci = 1 / (1+(n-ns+1) / (ns*lowf)); * lower CI for response rate;  
upp_ci = 1 / (1+(n-ns) / ((ns+1)*uppf)); *upper CI for response rate;  
if p=1 then upp_ci=1;  
if p=0 then low_ci =0;  
output;  
end;run;
```

Toxicity Probability Interval (TPI) Bayesian Design:

Expansion phase of the study will use a TPI Bayesian model utilizing data of all current DLT-evaluable subjects. It will evaluate the appropriateness of the preliminary MTD from dose exploration.

The MTD target TPI for DLT is (0.20, 0.35), and TPIs of (0.35, 0.60) and (0.60, 1.00) are defined as excessive and unacceptable, respectively. The design seeks to identify a dose most likely to have a DLT rate in the target TPI, but with overdose control that limits the possibility the dose has an excessive or unacceptable DLT rate (Babb et al, 1998).

The probability of a DLT at dose level d_i is assumed to follow a Bernoulli distribution with probability p_i where the logit of p_i increases linearly with the log of the standardized dose in the following 2-parameter logistic model:

$$\log\left(\frac{p_i}{1-p_i}\right) = \text{logit}(p_i) = \log \alpha + \beta \log\left(\frac{d_i}{d_{max}}\right)$$

where α and β are random variables and d_{max} is the maximum planned dose.

A minimally informative prior distribution (Neuenschwander et al, 2008) was selected for $\theta = (\log \alpha, \log \beta)$ where the probability that the true DLT rate is ≤ 0.60 at the lowest dose (30 mg Q3W) is 0.90 and the probability the true DLT rate is ≤ 0.20 at the maximum dose (██████ Q3W) is 0.21. These values were selected such that p_i is around 0.275 for 105 mg dose level, which is approximately in the median of the planned dose range.

Median values for p_i were interpolated per the logistic model. For each d_i , 2 quantiles for p_i were selected from a Beta distribution with the target median and a precision less than 2. This set of quantiles fully specified a target prior for theta. A bivariate normal distribution for theta was assumed where $\log \alpha$ has a normal distribution with mean μ_α and standard deviation s_α , and $\log \beta$ has a normal distribution with mean μ_β and standard deviation s_β , and γ is the correlation between $\log \alpha$ and $\log \beta$. Numerical integration with the SAS QUAD function was used to calculate $\Pr[p_i \leq q(d_i)]$, where $q(d_i)$ is a quantile for dose d_i . An optimal bivariate normal distribution was estimated that achieved the minimum sum of squared difference between achieved and specified quantiles across all doses using a non-linear optimization by a quasi-Newton method with the SAS IML NLPQN function. The bivariate normal distribution prior solution has $\mu_\alpha = 0.0536$, $s_\alpha = 1.685$, $\mu_\beta = -0.1469$, $s_\beta = 1.001$ and $\gamma = -0.216$.

The operating characteristics of the TPI Bayesian design will be evaluated at each dose using accumulated data of DLT evaluable subjects. Here, two parameters logistic regression would be fitted to accumulated data of all DLT evaluable subjects from dose exploration and expansion phase. $\text{Theta} = (\log a, \log b) \sim \text{BVN}$ with parameters information mentioned above (use of prior). Theta would be estimated and would be used to estimate pi for each of d_i using 2 parameter logistic model. Pi for each of d_i would be compared with MTD target TPI for DLT. An "acceptable" final dose was defined as one with the highest or second highest target TPI probability and a less than 0.25 excessive or unacceptable TPI probability.

DLRM Outputs List:

Listings:

1. Subject demographics
2. Date, time, dose of investigational product administration
3. Electrocardiogram (ECG) results, change from baseline
4. ECHO or MUGA results
5. Vital signs
6. Reported adverse events (AEs)
7. Safety laboratory data (chemistry, hematology, urinalysis, coagulation)
8. Current malignancy
9. Medical history
10. Concomitant medications
11. Prior anti-cancer therapy and prior radiotherapy data
- 12. Quantification of Immunoglobulins**
- 13. SPEP**

Figures

1. Line plot of vital signs by time course
2. Line plot of all safety labs by time course
3. Line plot of ECGs results by time course
4. Plot of the posterior probability of DLT (Expansion phase)
5. Distribution plot of the predicted MTD (Expansion phase)
6. Bar chart of the number of subjects studied per dose in dose exploration phase
7. **Protein_M1 line plot**

